- Cardiorespiratory Function: Recordings will be collected using a portable cardiovascular autonomic cart at CaronTC. The data will be recorded via a data acquisition system (PowerLab, ADInstruments). After instrumentation, participants will rest for 10 minutes, followed by 15 minutes of continuous recordings of cardiorespiratory parameters.
 - Blood pressure, heart rate, and respiratory rate will be measured at baseline (Day 1), during study drug administration (Days 2, 8, 14, 19, 20, 26, and 31), and at the end of rebound follow-up (Day 21 [Day 33 for 5-dose intervention]). At each of these time points, participants will be placed in the supine position.
 - Blood pressure will be measured continuously using the finger volume clamp method (NOVA Finapres Medical Systems or similar) and intermittently by an oscillometric brachial artery cuff (Philips SureSigns VS3 or similar).
 - A 3-lead EKG will be used to continuously measure heart rate (Cardiocap/5 GE Healthcare or similar).
 - Respiratory rate will be measured using a pneumography belt, and oxygen saturation by pulse oximeter applied to the finger (BCI 3301 or similar).
- Cue-elicited drug craving will be evaluated. This will be evaluated using Visual Analog Scales (VAS) on Day 1 and Day 19 [and additionally at Day 31 for 5-dose intervention].
 - Cue-elicited craving will be measured on a 0-100 point VAS, where 0= no craving, 100 = maximum craving. Assessments will be taken prior to, and immediately after, exposure to visual drug cues in the Cue Response Task.
- Ecological Momentary Assessment (EMA): EMA data will be collected throughout the study (Days 1-21 [Days 1-33 for 5-dose intervention]) 4 times per day via smartphones for the first 3 days (Days 1-3) and then on a rotating "4-days on, 2-days off" schedule starting Day 6. Data to be collected include: Ambient Drug Craving; Positive and Negative Mood; Pain/Discomfort; and Sleep on 0-100 point VAS.

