The smartphones that will be used for EMA data collection will have an app (the Wear-IT app) that will be put on the study smartphone provided to the participant while they are in the study. This smartphone will have a security application installed that prevents user access to all other applications that are not associated with data collection. Smartphones will not be activated on a cellular network resulting in the disabling of voice, text, and internet functions. Research staff will use brief in-person meetings (every other day) as a means to ensure devices are being charged, build rapport, answer participant questions, monitor compliance, and to manually download data for backup storage for upload to a secure server, Virtual COLO, at University Park in State College. Participants will need to plug the phone in to charge each night.

 Physiological Wearables: A "wearable" wristband will be worn throughout the study (Days 1-21 [Days 1-33 for 5-dose intervention]) to monitor stress responses, including acute

changes that may be associated with the drug delivery via injection. Data collected include heart rate, actigraphy for sleep and activity measurement, and stress responses (including acute changes in these measures that may be associated with the drug delivery via injection). A body temperature compliance sensor will be used to validate that the device is being worn. So that participants do not have to charge the actigraphy wristband themselves, participants will have up to two actigraphy wristbands assigned to them, and they will be charged or, if necessary, swapped out at their check-in sessions. Participants may wear the actigraphy wristband while showering or swimming if they wish.

- Neurophysiology Lab Day Measures: Participants will be tested at baseline (Day 1) and at the end of the target dose (Day 19 [and additionally Day 31 for 5-dose intervention]) for cortical activity using Functional Near Infrared Spectroscopy (fNIRS) and VAS during:
 - Visual cue reactivity task to: (a) opioid cues; (b) non-opioid control cues; (c) natural reward cues (e.g., pleasant pictures of food, puppies, positive relationships, etc.) and (d) emotionally neutral stimuli (e.g., images of household objects)
 - The VAS measure of craving pre-post visual cue reactivity task
 - Balloon Analogue Risk Task (BART)

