8.2 Sample size determination

This is an exploratory study to accumulate pilot data. The primary endpoint of this study is cue-elicited self-reported craving VAS scores. A sample size of N=20 per group will give 80% power to detect an effect size of 0.91 based on a two-sided two-sample t-test with a significance level of alpha=0.05. Accounting for an estimated 20% attrition rate, we plan to randomize a total of 20*2/0.8=50 patients in the study. To preserve statistical power, the sample will not be balanced with regard to MAT and non-MAT participants.

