8.3 Statistical methods

The primary aim is to test whether liraglutide reduces craving in patients recovering from OUD in residential treatment. Analysis of covariance (ANCOVA) will be used to compare liraglutide versus placebo treatment groups controlling for baseline values of craving. Linear mixed effects models for repeated measurements will also be used to evaluate the difference in changes in these primary outcomes between treatment groups. The baseline and post-treatment outcomes are treated as dependent variables in the mixed model. Subjects with missing values can be incorporated in the mixed model analysis when data are missing at random. The moderating effect will be assessed by adding the interaction term between moderator and treatment group in the models.

SAS (version 9.4) and R (version 3.2.5) software will be used for analyses with a significance level of 0.05. Summary statistics including means, medians, ranges, and standard deviations will be computed for each continuous variable and frequencies with percentages for categorical variables. Identified data outliers will be further examined to determine if they are data entry errors, in which case they will be modified when possible; otherwise, values will be kept for final analysis.

Primary outcomes to assess efficacy are: (1) cue-elicited drug craving rated on a 100-pt VAS; and (2) ambient drug craving, derived from EMA of daily craving throughout the study period. Data analyses for cue-elicited craving will consist of a 2×2 ANOVA with medication status (pre- vs post-medication) as a within-group variable and medication type (liraglutide vs placebo) as a between-group variable.

Secondary analyses of self-reported craving measures will evaluate the role of MAT, specifically BUP/NA, in these results.

EMA and Wearable Assessment: Ambient drug craving derived from the EMA will be analyzed as a multilevel model in the regression framework and will test effects of medication status within-person and medication type between-person. Secondary analyses of EMA will examine the effect of time (e.g. study day) to identify differences across condition in the rate of decline in craving across time.

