Data reduction including derivation of summary features for continuously collected data (e.g., sleep data, physiological data) will be performed before formal statistical analysis. Descriptive analysis will be performed to explore distributions of data and identify potential outliers. Assumptions and goodness of fit of statistical models will be assessed. Missing data, including mobile and ambulatory attrition and drop-out will be examined to ensure the validity of statistical models used. Because ambulatory and mobile monitoring will continue during laboratory assessment days, correlation analyses will be used to confirm the agreement between corresponding measures from the two approaches; this will both speed harmonization for follow-up analyses, and provide additional validation of the measures used in the both cases.

The primary endpoints of the EMA assessment will be the rate of reduction of craving across the approximately 21 day study period in the treatment condition compared to the control condition while controlling for the traditional craving triggers of sleep, stress, hunger, affect, and pain and discomfort. Sleep and activity will be measured using a multimodal approach with self-report via the morning EMA survey and wearable actigraphy to measure and account for subjective biases in sleep timing. Craving reduction will be primarily measured using EMA assessment, and will be modeled using linear mixed models in the multilevel modeling (MLM) framework. In MLM, subject-specific random effects are combined with population-level fixed effects to account for variability both within each individual and between individuals in a manner that allows participants with incomplete data to be included in the model. Craving reduction will be modeled as an effect of time in treatment, and differences in rate of craving reduction will be tested as an interaction between treatment state and time. Drs. [name], [name], and [name] each have extensive experience analyzing similar data in the multilevel modeling framework.

For secondary safety outcomes, intensive longitudinal methods such as time-varying effect models will be used to assess for changes in continuously measured outcomes (e.g. blood pressure, heart rate, respiratory rate, body weight) to account for repeated measures. The proportion of participants experiencing AE and SAE will be compared between treatments using chi-square analysis.

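### Correlation cannot confirm that wearable or mobile measures agree with laboratory measures; same-unit pairs need a mean difference and limits of agreement

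*Combined protocol and SAP*

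**What the plan says.** The EMA and wearable part of Section 8.3 (Statistical methods) explains when paired data arise: "Because ambulatory and mobile monitoring will continue during laboratory assessment days". It then names the method and its purpose: "correlation analyses will be used to confirm the agreement between corresponding measures from the two approaches". Two uses follow: "this will both speed harmonization for follow-up analyses, and provide additional validation of the measures used in the both cases".

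Section 8.3 does not say which correlation coefficient will be used, what value would count as agreement, or which measures correspond. For this comparison it plans no mean difference, limits of agreement, intraclass or concordance coefficient, or calibration step.

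Two nearby statements do not fill the gap:
- General description: "Summary statistics including means, medians, ranges, and standard deviations will be computed for each continuous variable". These are summaries of each variable, not of paired differences.
- The only remark on measurement bias concerns self-reported sleep against "wearable actigraphy to measure and account for subjective biases in sleep timing". That is not a mobile-versus-laboratory comparison.

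The clearest pair is heart rate. For the wristband, Section 7.2 states "Data collected include heart rate, actigraphy for sleep and activity measurement, and stress responses". For the laboratory assessment it states "A 3-lead EKG will be used to continuously measure heart rate".

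**The concern.** Agreement means that two methods give nearly the same value for the same person at the same time. Correlation asks only whether the values rise and fall together. Pearson's r is unchanged by adding a constant to one method or multiplying it by a positive factor, and rank correlation is unchanged by any increasing transformation. Whichever coefficient is meant, the stated method cannot support the stated conclusion.

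The reverse error is also possible. Correlation depends on how much people differ from one another, so two methods that agree well can show a low r in a homogeneous group.

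At stake is the statement that the measures were validated, which could carry into the larger trial this pilot is meant to inform (Section 2.3). Also at stake is any follow-up analysis that combines the two sources. For example, a participant with an EKG value on Day 1 and a value from a wristband reading 10 bpm high on Day 19 would show a 10 bpm change from the switch of device alone.

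**Working it through.** **The plan's own figure.** The agreement check has no stated figure. The only design calculation is in Section 8.2: "A sample size of N=20 per group will give 80% power to detect an effect size of 0.91". It reproduces: a two-sided two-sample t-test at alpha 0.05 with 20 per group and d = 0.91 has power 80.1%, and 20 × 2 / 0.8 = 50. So about 40 completers can be expected, and 40 is used below as the number of pairs, one per participant.

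**Assumed inputs (not in the documents).** Laboratory heart rate has mean 75 and SD 10 bpm. The device errors are as stated in each case. That r does not respond to an offset holds for any values; only the sizes depend on these assumptions.

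**Case 1: constant offset.** Device = laboratory + 10 + error, error SD 3.3.
- Device variance = 100 + 3.3² = 110.89, so SD = 10.53.
- r = 100 / (10 × 10.53) = 0.95.
- Mean difference = 10. Limits = 10 ± 1.96 × 3.3 = 10 ± 6.47, or +3.5 to +16.5 bpm.
- Concordance = 2 × 100 / (100 + 110.89 + 10²) = 200 / 310.89 = 0.64.

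**Case 2: compressed scale.** Device = 0.5 × laboratory + 37.5 + error, error SD 1.65.
- Device variance = 25 + 1.65² = 27.72, so SD = 5.27.
- r = 50 / (10 × 5.27) = 0.95.
- Mean difference = 0.5 × 75 + 37.5 − 75 = 0. The difference has variance 0.25 × 100 + 2.72 = 27.72, so the limits are ±1.96 × 5.27 = ±10.3 bpm.
- Here the mean difference alone would also miss the fault; the limits show it.

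**Case 3: error in both methods.** Between-person SD 10, error SD 3 in each method, offset a. Then r = 100 / (100 + 9) = 0.917 for every a. Concordance = 200 / (218 + a²). Limits = a ± 1.96 × √18 = a ± 8.3.

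| Offset (bpm) | r | Concordance | 95% limits |
|---|---|---|---|
| 0 | 0.917 | 0.917 | −8.3 to 8.3 |
| 5 | 0.917 | 0.823 | −3.3 to 13.3 |
| 10 | 0.917 | 0.629 | 1.7 to 18.3 |
| 20 | 0.917 | 0.324 | 11.7 to 28.3 |

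**Case 4: the reverse error.** No offset, the same errors, between-person SD 2: r = 4 / (4 + 9) = 0.31, with the same limits of −8.3 to 8.3. Concordance also falls to 0.31, so a decision to combine should rest on the limits.

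**Can the check tell the devices apart?** In 5,000 simulated trials of 40 pairs under Case 3, r was at least 0.8 in 99.8% of runs with an offset of 10 or 20 bpm, against 99.9% with none. A paired test of the mean difference found the offset in 100% of runs. With 40 pairs, r need only exceed 0.31 to be significant at 0.05.

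**Is the alternative feasible at this size?** The 95% confidence half-width of each limit, in SDs of the differences, is 1.96 × √(1/40 + 1.96² / (2 × 39)) = 0.53 (0.48 with 50 pairs). In Case 1 that is 0.53 × 3.3, about 1.8 bpm.

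**Could it reach the treatment effect through a covariate?** Section 8.3 adjusts the EMA craving model for sleep and stress, both of which the wristband records. If a covariate is recorded as Z′ = c + dZ for everyone, then βZ = (β/d)Z′ − βc/d. The covariate's slope and the intercept change; the treatment-by-time coefficient does not.

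**The case against.** The strongest reply is that little rests on this sentence. Sections 1.2 to 1.4 list no wristband endpoint. Craving is self-reported on a VAS. The heart-rate endpoint and the withdrawal criteria in Sections 3.3.1 and 18.7 use the scheduled cardiorespiratory measurements, with heart rate from the 3-lead EKG. The study is an exploratory pilot. All of this stands and limits the consequence, but it does not make correlation a measure of agreement.

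A reader might infer more than the documents support:
- **That a biased device would be accepted and the sources used interchangeably.** The plan has no acceptance rule, and harmonisation can equally mean calibrating one scale to the other. A large offset might also be noticed in the unpaired means. The supportable statement is that such a device could be accepted.
- **That the craving or safety results would be biased.** Those outcomes come from other measurements. A uniform offset or rescaling of a single-source covariate leaves the treatment-by-time effect unchanged in a linear model with fixed covariate effects.
- **That repeated readings will be pooled across people.** Section 8.3 does not say so. It plans data reduction to summary features first, and multilevel models for EMA.

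A further objection concerns the remedy and also stands. Some possible pairs are not the same quantity, such as ambient EMA craving against craving before and after laboratory cues, or wristband stress responses against laboratory physiology. Limits of agreement mean nothing there, and correlation is a reasonable measure of association.

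**Conclusion.** The point holds as a mismatch between method and conclusion. Correlation is the only analysis named for confirming agreement, and it cannot detect a constant offset or a compressed scale. Under the assumed heart-rate values, r stays at 0.917 for offsets from 0 to 20 bpm while concordance falls from 0.917 to 0.324. Real device errors are unknown and may be smaller.

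The consequence is confined to the validation claim and to follow-up analyses that combine mobile or wearable data with laboratory data. It should be corrected before analysis because the change is cheap, but it is not a threat to the trial's main results.

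**What to change.** Amend the sentence in Section 8.3 as follows.

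1. List the corresponding pairs, with units and the days on which both are measured.
2. For pairs of the same quantity in the same units, such as wristband and 3-lead EKG heart rate, report the mean difference and 95% limits of agreement. Take them from a mixed model of the paired differences with a participant effect, so that repeated assessment days are handled properly. Examine whether the difference varies with the level, and add a concordance coefficient as support.
3. Set an acceptable difference for each such pair in advance, with its justification. Combine sources only if the limits fall inside it; otherwise calibrate or analyse them separately. State whether the rule uses the estimated limits or their confidence bounds.
4. For all other pairs, keep correlation but describe it as association, not agreement or validation.

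The data and sample size do not change. The cost is a wording amendment, minor programming, and the work of justifying an acceptable difference, for which the documents give no basis.

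### Section 8.3 gives two different primary results for EMA craving, and adjusts one of them for craving triggers without stating the timing or form of those covariates

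*Combined protocol and SAP*

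**What the plan says.** Ambient craving measured by EMA is one of two primary outcomes in sections 1.2 and 8.3. Section 1.2 defines it only as change over time, with no summary measure and no covariates.

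Section 8.3 then describes several analyses that could deliver the EMA result:

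- For the primary outcomes generally: "Analysis of covariance (ANCOVA) will be used to compare liraglutide versus placebo treatment groups controlling for baseline values of craving", and "Linear mixed effects models for repeated measurements will also be used to evaluate the difference in changes in these primary outcomes between treatment groups".
- In the EMA and Wearable Assessment paragraph, a multilevel model that "will test effects of medication status within-person and medication type between-person". The same paragraph continues: "Secondary analyses of EMA will examine the effect of time (e.g. study day) to identify differences across condition in the rate of decline".
- In a later paragraph, the primary EMA endpoint is the between-arm difference in the rate of craving reduction over about 21 days, "while controlling for the traditional craving triggers of sleep, stress, hunger, affect, and pain and discomfort". There, "differences in rate of craving reduction will be tested as an interaction between treatment state and time".

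On where the covariates come from, the later paragraph says: "Sleep and activity will be measured using a multimodal approach with self-report via the morning EMA survey and wearable actigraphy". Section 7.2 lists craving, mood, pain/discomfort and sleep as EMA items and takes stress responses and sleep from the wristband, all collected throughout dosing. No section describes a hunger measure.

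**The concern.** Two questions are left open for a primary outcome.

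The first is which EMA contrast is primary. The rate of decline is secondary in one paragraph of 8.3 and primary in another. Section 1.2 does not settle it.

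The second is what the adjusted slope estimates. The stated aim in 8.3 is to test whether liraglutide reduces craving. If a covariate is measured after dosing, varies over time and is itself changed by the drug, holding it fixed removes the part of the effect that passes through it. The plan expects this for at least one trigger: section 23.0 hypothesises longer sleep on liraglutide and asks whether better sleep goes with less craving. Section 10.0 lists nausea and decreased appetite as common side effects, which bear on discomfort and hunger.

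As written, the reported EMA result could be an adjusted slope, an unadjusted slope or a pre/post contrast. These answer different questions, and nothing stops the choice being made after the data are seen. Section 8.3 also uses confidence intervals around the primary-endpoint parameters when deciding whether to run an interim analysis. If an EMA parameter is among them, the plan does not say which.

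**Working it through.** **1. The label conflict.** One paragraph of 8.3 puts between-arm differences in rate of decline under secondary EMA analyses. The later paragraph makes the same quantity the primary EMA endpoint. Both cannot stand.

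**2. The two contrasts are different quantities.** EMA days in the 3-dose schedule (schedule of activities, footnote 7) are 1–3, 6–9, 12–15 and 18–21: 3 + 4 + 4 + 4 = 15 days. Dosing starts on Day 2 (section 7.2), so 14 of 15 are on or after the first dose. At 4 prompts a day that is 56 of 60 prompts. The 5-dose schedule adds Days 24–27 and 30–33: 23 days, 22 on or after Day 2.

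The 14 later days sum to 167 and average 167/14 = 11.93. An effect growing linearly from Day 1 therefore averages (11.93 − 1)/18 = 0.607 of its Day 19 value. If the off-drug Days 20–21 are left out, the mean day is 126/12 = 10.5 and the fraction is 9.5/18 = 0.528. This is not an error size. It shows only that a pre/post contrast and a slope summarise the same effect differently, so the choice must be declared.

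**3. What concurrent adjustment does to the slope.** Let the total between-arm effect on craving, expressed as a slope scaled to Day 19, be T. Let b be the craving change per trigger point, and A the drug's effect on the trigger, expressed as its least-squares slope over the EMA days and scaled to 18 days. With complete data and person-specific intercepts and slopes:

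adjusted coefficient = T − A × b.

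It equals T only if A = 0 or b = 0. The documents give neither A nor b. The following rows use assumed values only: T = −10 VAS points and a peak trigger effect of 10 points. The mean EMA day is 168/15 = 11.2, and the sum of squared deviations is 2504 − 15 × 11.2² = 622.4.

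| Assumed drug effect on trigger | A | b | Adjusted coefficient |
|---|---|---|---|
| None | 0 | any | −10 |
| Sleep better, growing linearly to Day 19 | 10 | −0.5 | −10 + 5 = −5.0 |
| Sleep better by a constant 10 from Day 2 | 18 × 102/622.4 = 2.95 | −0.5 | −10 + 1.5 = −8.5 |
| Discomfort 10 higher on Day 2, fading linearly to 0 by Day 19 | −6.98 | +0.5 | −10 + 3.5 = −6.5 |
| Discomfort growing linearly to Day 19 | 10 | +0.5 | −10 − 5 = −15 |

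The last two rows share the sign of b and differ only in time course, yet they move the estimate in opposite directions.

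**4. Forms that leave the slope alone.** Day 1 trigger values cannot carry a drug effect. In simulation under assumed variances, adjusting for them left the estimate at the unadjusted value (both −9.9). A post-dose person-level mean entered only as a main effect shifts the intercept, not treatment by time; in simulation it gave −9.8 against −10.2 without it, equal within simulation error.

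**5. Precision.** Assumed: 20 per arm, random-slope SD 8 (Day 19 scale), residual SD 10, within-person trigger SD 10, b = 0.5.

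SE = √[(2/20)(8² + 18² × s²/622.4)], where s² is the residual variance left in the model.

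- Triggers adjusted, s² = 100: SE = 3.41.
- One trigger left out, s² = 100 + 25 = 125: SE = 3.59. Adjustment lowers it by 5%.
- Five independent triggers left out, s² = 100 + 125 = 225: SE = 4.26. Adjustment lowers it by 20%.

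**The case against.** **Unadjusted models are already planned.** The ANCOVA, the mixed models and the status-and-type model in 8.3 name no triggers. A reader might infer that the plan contains no unadjusted EMA estimate; that is not so. But none of these is consistently labelled primary for EMA, and the one paragraph that defines a primary EMA endpoint adjusts for triggers.

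**Timing and form are unstated, not misstated.** 8.3 says that summary features of sleep and physiological data will be derived before formal analysis, and a person-level summary used as a main effect would do no harm to the slope. This stands. A reader might infer that any use of post-dose trigger data distorts the result. Only covariates that vary over time and that the drug changes do so.

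**The direction is not known.** A reader might infer that adjustment dilutes the drug effect through sleep, or inflates it through discomfort. Neither follows. Section 23.0 is aware of no human data on sleep architecture under this drug class. Section 10.0 says the common gastrointestinal effects dissipate over time, which makes the inflated row in the table the less natural one. Whether the pain/discomfort item captures nausea is not stated.

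**A slope beyond known triggers may be wanted.** Total effect is a statistician's term and does not appear in 8.3. An adjusted slope is a legitimate mechanistic question, but it does not fully answer whether liraglutide reduces craving, which is the stated aim.

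**Hunger may be measured though unlisted.** The EMA list in 7.2 need not be exhaustive: section 23.0 mentions sleep inventories in the parent study that 7.2 does not list. This supports a request for clarification, no more.

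**This is a pilot.** In section 8.2, "The primary endpoint of this study is cue-elicited self-reported craving VAS scores". That narrows the impact but does not remove the conflict.

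**Conclusion.** The conflict within 8.3 over the primary EMA result is explicit and rests on no assumption. The covariate point is conditional: if the triggers enter as concurrent, time-varying values, which is the natural reading because sleep comes from a repeated morning survey and actigraphy, the treatment-by-time coefficient excludes any effect on the craving slope that works through a trigger the drug changes. It would then not fully answer the primary question.

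No size or direction can be given. The documents state neither the drug's effect on any trigger nor the trigger–craving relation, and the answer depends on the time course. The figures in the table are illustrations on assumed inputs and carry no weight for severity. A reader might go further and infer that the trial's primary conclusion is compromised. The documents do not support that: cue-elicited craving, on which section 8.2 sizes the trial, is untouched, and so is the sample size. This should be fixed before analysis, and the change is small.

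**What to change.** In section 8.3:

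1. Name one EMA contrast as primary, either status by type or treatment by time (the sponsor's choice), and use the same label in both paragraphs.
2. Fit that primary model without post-dose trigger covariates. Allow at most pre-dose values: Day 1 for EMA items and, for sleep, the night before the first dose, which the wristband started on Day 1 (section 7.2.1) can record.
3. Keep the model with time-varying triggers as an exploratory or mechanistic analysis. State the form and timing of each covariate, and state that its treatment coefficient is not the total effect on craving.
4. Name the source of the hunger measure, or delete hunger from the list.

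The assessment window in section 1.2 need not change. The cost is wording, with no new visits or data unless a hunger item is added. The primary model gives up the precision that concurrent triggers would have bought: under the assumed variances above, a standard error reduction of about 5% with one trigger to 20% with five, and less if the triggers are weaker. That precision remains available in the exploratory model.
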